6.5.3. Procedures for Participants Exhibiting Immune-Related Adverse Events

Adverse events of a potential immunologic etiology, or irAEs, may be defined as AEs of unknown etiology, associated with drug exposure and consistent with an immune phenomenon. Immune-related AEs may be predicted based on the nature of the compounds, their mechanism of action, and reported experience with immunotherapies that have a similar mechanism of action. Special attention should be paid to AEs that may be suggestive of potential irAEs. An irAE can occur shortly after the first dose or several months after the last dose of treatment.

If an irAE is suspected, efforts should be made to rule out neoplastic, infectious, metabolic, toxic, or other etiologic causes before labeling an AE as an irAE.

General recommendations for the management of specific irAEs known to be associated with other PD-1 inhibitors (eg, pembrolizumab, nivolumab) are detailed in [Table 11](#). Algorithms for evaluation of selected immune toxicities that have previously been attributed to PD-1 inhibitors and management guidelines for irAEs not detailed elsewhere in the protocol should follow the ASCO or ESMO Clinical Practice Guidelines ([Haanen et al 2017](#), [Schneider et al 2021](#)).

Continuous evaluation of toxicity events will be performed throughout the study to assess for any late-onset immune-related toxicities that occur up to a minimum of 90 days after the last dose of study drug. If warranted, enrollment of participants may be suspended until the sponsor, investigators, and DSMB have determined the appropriate course of action.

Table 11: Guidelines for Management of Immune-Related Adverse Events

irAE	Toxicity Grade or Conditions (CTCAE v5.0)	Action Taken With Study Treatment	Adverse Event Management With Corticosteroid and/or Other Supportive Care Therapies
Pneumonitis	Grade 1	No action.	None.
	Grade 2	Withhold until \leq Grade 1.	
 Administer systemic corticosteroids per local practice followed by taper. Evaluate participants with suspected pneumonitis with radiographic imaging and initiate corticosteroid treatment. Add prophylactic antibiotics for opportunistic infections.
	Grades 3 or 4, or recurrent Grade 2	Permanently discontinue.	
Diarrhea/colitis	Grade 1	No action.	None.
	Grades 2 or 3	Withhold until \leq Grade 1.	
 Consider prompt initiation of standard antidiarrheal agents and other necessary supportive care as needed (eg, oral and/or IV fluids). Administer systemic corticosteroids per local practice followed by taper. Consider prophylactic antibiotics per local practice. Consider gastrointestinal consultation and performing endoscopy to rule out colitis.
	Grade 4 or recurrent Grade 3	Permanently discontinue.	
AST/ALT elevation and/or increased total bilirubin/hepatitis	Grade 1	No action.	
 Administer systemic corticosteroids per local practice followed by taper. Consider monitoring liver enzymes weekly (or more frequently) until liver enzyme value returns to baseline or is stable. Consider monitoring total bilirubin, direct bilirubin, and alkaline phosphatase weekly (or more frequently) if needed.
	Grade 2 ALT or AST increase or Total bilirubin increases to $> 1.5 \times$ and up to $3 \times$ ULN	Withhold.	
	Grades 3 or 4 ALT or AST increase or In participants with liver metastases with baseline Grade 2 elevation of AST or ALT, hepatitis with AST or ALT increases $\geq 50\%$ and lasts ≥ 1 week or Total bilirubin increases to $> 3 \times$ ULN	Permanently discontinue.	

Table 11: Guidelines for Management of Immune-Related Adverse Events (Continued)

irAE	Toxicity Grade or Conditions (CTCAE v5.0)	Action Taken With Study Treatment	Adverse Event Management With Corticosteroid and/or Other Supportive Care Therapies
Endocrinopathies 
 Type 1 diabetes mellitus Hyperglycemia Hyperthyroidism Hypothyroidism Adrenal insufficiency 	Grades 1 and 2	No action if clinically appropriate.	None.
	Grade 2 adrenal insufficiency	Withhold until \leq Grade 1 or otherwise clinically stable	Initiate treatment with HRT as clinically indicated.
	Grades 3 and 4 adrenal insufficiency	Withhold until \leq Grade 1 after corticosteroid taper to \leq 10 mg/day prednisone or equivalent or is otherwise clinically stable.	Initial dose of 1 to 2 mg/kg/day prednisone or equivalent followed by a taper and HRT as clinically indicated.
	Grades 3 and 4 hypothyroidism	Withhold until \leq Grade 2 or is otherwise clinically stable.	Initiate thyroid replacement hormones (eg, levothyroxine or liothyronine) per SoC.
	Grades 3 and 4 hyperthyroidism	Withhold until \leq Grade 2 or is otherwise clinically stable.	Initiate symptomatic management.
	Grades 3 or 4 type 1 diabetes mellitus (or hyperglycemia)	Withhold until \leq Grade 1 or is otherwise clinically stable.	Initiate treatment with antihyperglycemics as clinically indicated.
Endocrinopathies 
 Hypophysitis 	Grade 1	No action.	None.
	Grade 2 (asymptomatic)	Withhold until \leq Grade 1. May restart study treatment after controlled by HRT.	Administer hormonal replacement.
	Grade 2 (symptomatic; eg, headaches, visual disturbances)	Withhold until \leq Grade 1. May restart study treatment after controlled with HRT, if indicated, and steroid taper is complete.	
 Administer corticosteroids at initial dose of 1 to 2 mg/kg/day prednisone or equivalent followed by a taper, and initiate other HRTs as clinically indicated. Consult with endocrinologist as needed.
	Grade 3 or 4 (symptomatic)	
 Permanent discontinuation should occur if after withholding study treatment, the toxicity does not resolve to \leq Grade 1 within 12 weeks after last dose of study treatment, or if corticosteroid dose cannot be reduced to \leq 10 mg prednisone or equivalent per day within 12 weeks. Permanent discontinuation should take place earlier at the investigator's discretion if corticosteroids and/or HRT cannot balance the participant's pituitary function. 	
 Administer corticosteroids at initial dose of 1 to 2 mg/kg/day prednisone or equivalent followed by a taper and initiate other HRTs as clinically indicated. Consult with endocrinologist as needed.

Table 11: Guidelines for Management of Immune-Related Adverse Events (Continued)

irAE	Toxicity Grade or Conditions (CTCAE v5.0)	Action Taken With Study Treatment	Adverse Event Management With Corticosteroid and/or Other Supportive Care Therapies
Nephritis with renal dysfunction	Grade 1	No action.	None.
	Grade 2 increased blood creatinine	Withhold until \leq Grade 1.	Administer corticosteroids per local practice followed by taper.
	Grade 3 or 4 increased blood creatinine	Permanently discontinue. ^a	
Skin (eg, Stevens-Johnson syndrome, or toxic epidermal necrolysis)	Grade 1	No action.	None.
	Grade 2	No action.	Manage with topical steroids with or without drug interruption.
	Grade 3 ^b or persistent Grade 2 (≥ 2 weeks) or suspected Stevens-Johnson syndrome ^c	Withhold until \leq Grade 1. Study treatment can be resumed at same dose.	
 Administer corticosteroids per local practice followed by taper. Additionally, oral antihistamines such as diphenhydramine or famotidine (per institutional preference) may be utilized as needed. Should refer to dermatology if no resolution with these measures.
	Recurrent Grade 3 ^d after resuming study treatment or Grade 4 rash or confirmed Grade 4 Stevens-Johnson syndrome ^c or toxic epidermal necrolysis ^e	Permanently discontinue.	
 Initial dose of 1 to 2 mg/kg/day prednisone or equivalent followed by a taper. Refer to dermatology consult.
Myocarditis	Grade 2	
 Depending on severity of symptoms withhold until symptoms fully resolve and management with corticosteroids is complete. Permanent discontinuation may take place earlier at the investigator's discretion. 	
 Treatment with systemic corticosteroids should be initiated (initial dose of 1 to 2 mg/kg/day of prednisone or equivalent). Taper as appropriate. Manage cardiac symptoms according to SoC and with guidance from cardiology. Consider cardiac MRI and myocardial biopsy for diagnosis.
	Grades 3 or 4	Permanently discontinue.	
TnI or TnT increase	All grades (including asymptomatic cases)	Withhold until cardiac evaluation is completed, myocarditis is ruled out, and a cardiologist recommends that treatment may proceed.	
 Refer to cardiology consult and initiate diagnostic workup including ECG, echocardiogram (plus cardiac MRI as needed for diagnostic confirmation), and further relevant biological markers (eg, BNP, CPK) as per the cardiologist recommendation. Confirmatory tests should be repeated within 24 hours 
 If troponin elevation is not confirmed within 24 hours in an asymptomatic participant, the dose delay may not be needed provided that the cardiac evaluation is completed and a cardiologist-recommended treatment may proceed. If troponin elevation is confirmed, continue serial monitoring and consider initiating corticosteroids per cardiologist recommendation. Study treatment may resume when the cardiac evaluation is complete, myocarditis is ruled out, and a cardiologist recommends that treatment may proceed.

Table 11: Guidelines for Management of Immune-Related Adverse Events (Continued)

irAE	Toxicity Grade or Conditions (CTCAE v5.0)	Action Taken With Study Treatment	Adverse Event Management With Corticosteroid and/or Other Supportive Care Therapies
Important nervous system events (eg, Guillain-Barre syndrome, autoimmune encephalitis, myasthenia gravis, autonomic neuropathy, or transverse myelitis)	Grade 2	Withhold until \leq Grade 1.	
 Neurology consultation is recommended for all neurologic irAEs \geq Grade 2. Treatment with systemic corticosteroids should be initiated (initial dose of 1 to 2 mg/kg/day of prednisone or equivalent). Taper as appropriate. For Grade 2 transverse myelitis, consider permanent discontinuation. Manage symptoms according to SoC and with guidance from neurology.
	Grades 3 or 4	Permanently discontinue.	
All other irAEs	Grade 2 or Grade 3 based on severity and type of reaction	Withhold until \leq Grade 1.	Based on severity of AE, administer corticosteroids.
	Recurrent Grade 3 or persistent Grade 2 and Grade 3	Permanently discontinue.	
	Grade 4	Permanently discontinue.	

^a If study drug(s) are implicated in the renal toxicity.

^b Participants with first onset of Grade 3 rash with desquamation, and/or mucosal involvement, requiring systemic steroids and not resolving or improving to \leq Grade 1 within 14 days must permanently discontinue study treatment.

^c Grade 3 Stevens-Johnson syndrome is defined as skin sloughing covering $< 10\%$ BSA with associated signs (eg, erythema, purpura, epidermal detachment, mucous membrane detachment). Grade 4 Stevens-Johnson syndrome is defined as skin sloughing covering 10% to 30% BSA with associated signs (eg, erythema, purpura, epidermal detachment, mucous membrane detachment).

^d Refers to single recurrence after first onset of Grade 3 that did not require systemic steroids and participant recovered and resumed study treatment. Investigators are required to define the medical term or type of "rash" as best as possible and not to enter in eCRFs the term generically as rash only. Severe skin rashes per CTCAE criteria are generally a rash that covers $> 30\%$ BSA and can be in the form of macules/papules or pustules; limiting self-care activities of daily living.

^e Toxic epidermal necrolysis is Grade 4 by definition and is defined as skin sloughing covering $\geq 30\%$ BSA with associated symptoms (eg, erythema, purpura, epidermal detachment).

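### In the Table 11 Skin block, confirmed Stevens-Johnson syndrome forces a permanent stop only at Grade 4; a first Grade 3 case that settles may restart at full dose unless footnote b or discretion stops it

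*Protocol*

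**What the plan says.** The Skin block of Table 11 (Protocol Section 6.5.3) names Stevens-Johnson syndrome and toxic epidermal necrolysis as its examples. Above uncomplicated Grade 2 it has two action rows.

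- **Withhold row.** Covers Grade 3 events (footnote b), Grade 2 lasting two weeks or more, and suspected Stevens-Johnson syndrome (footnote c). Treatment is held until Grade 1 or less, and then "Study treatment can be resumed at same dose". Corticosteroids are directed. On dermatology the row says "Should refer to dermatology if no resolution with these measures".
- **Stop row.** Covers recurrent Grade 3 (footnote d) "after resuming study treatment or Grade 4 rash or confirmed Grade 4 Stevens-Johnson syndrome", and toxic epidermal necrolysis.

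Three footnotes matter.

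- **Footnote b** forces a permanent stop for a first Grade 3 rash with desquamation or mucosal involvement, "requiring systemic steroids and not resolving or improving to" Grade 1 or less within 14 days.
- **Footnote c** separates the grades. It begins "Grade 3 Stevens-Johnson syndrome is defined as skin sloughing covering" less than 10% of body surface, and puts Grade 4 at 10% to 30%.
- **Footnote d** explains the recurrence trigger: "Refers to single recurrence after first onset of Grade 3 that did not require systemic steroids and participant recovered and resumed study treatment".

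Section 6.5.1 does not allow dose modification. After an interruption for a treatment-related event, the study drugs restart at the starting dose.

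**The concern.** The table recognises Grade 3 Stevens-Johnson syndrome as a distinct entity but does not place it among the permanent stops. Confirming the diagnosis at that grade changes nothing by itself. What decides is whether the event settles.

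A participant whose confirmed Grade 3 case improves quickly may therefore be re-exposed to every assigned study drug at full dose: retifanlimab in all groups, plus INCAGN02385 and INCAGN02390 or their placebos according to blinded assignment. Preventing this depends on someone choosing to stop, against a table row that says resumption is allowed.

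Two related gaps sit in the same block. Resumption after a suspected case is not conditional on excluding the diagnosis. Footnote d, taken literally, confines the recurrence stop to first onsets managed without systemic steroids, although the withhold row directs corticosteroids for those events.

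**Working it through.** No statistical figure underlies this point, so the check traces a case through the rules.

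**1. Confirmed first-onset Grade 3 Stevens-Johnson syndrome (under 10% of body surface)**

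| Rule | Applies? |
|---|---|
| Stop row: recurrent Grade 3 | No, first onset |
| Stop row: Grade 4 rash or confirmed Grade 4 Stevens-Johnson syndrome | No, Grade 3 |
| Stop row: toxic epidermal necrolysis | No; Grade 4 by definition, sloughing of 30% or more (footnote e) |
| Withhold row: Grade 3 | Yes |
| Footnote b | Only if systemic steroids were required and the event is not at Grade 1 or less by day 14 |

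Footnote b is worded for rash, but its signs overlap those of Stevens-Johnson syndrome in footnote c, so I read it as covering these cases. That is the reading more favourable to the plan. The outcomes are:

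- improved to Grade 1 or less within 14 days: restart allowed;
- systemic steroids required and not improved by day 14: mandatory stop;
- systemic steroids not required and slower to settle: no footnote b stop. Section 6.5.1 limits interruptions to 28 days unless the sponsor approves longer, and Section 6.5.4 sets an outer limit for immune-related events of 12 × 7 = 84 days from the last dose. This branch is narrow because the row directs corticosteroids.

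**2. Suspected case.** It shares the withhold row. The condition for restart is the grade, not exclusion of the diagnosis. The troponin block does require myocarditis to be ruled out, and a cardiologist to recommend it, before treatment resumes. The sentence in Section 6.5.3 on ruling out other causes concerns labeling an event as immune-related. It does not ask for Stevens-Johnson syndrome to be excluded.

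**3. Recurrence.** The Skin stop row names recurrent Grade 3 without restriction, but footnote d narrows it. Colitis ("Grade 4 or recurrent Grade 3") and all other immune-related events ("Recurrent Grade 3 or persistent Grade 2 and Grade 3") stop recurrent Grade 3 with no steroid condition.

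**4. Precedent in Table 11.** There are 11 blocks, so 11 − 1 = 10 besides Skin.

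- Permanent stop at first Grade 3: pneumonitis, AST/ALT/hepatitis, nephritis (if study drug is implicated), myocarditis, nervous system events = 5.
- No automatic stop at first Grade 3: colitis, general endocrinopathies, hypophysitis, troponin, all other immune-related events = 5.

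**5. Exposure.** Sections 2.2.3 and 2.2.4 list immune-related events for 40 + 10 + 17 = 67 participants, with no Stevens-Johnson syndrome. Only the 17 on the triplet received retifanlimab. Section 2.2.1 reports 660 participants on retifanlimab monotherapy without a count for this event. Section 2.2.2 reports 22 on INCAGN02385 alone, with no related serious events. No usable rate follows.

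**The case against.** The best case for the plan is that no standard within the documents is breached. Footnote c grades the syndrome, and the stop row then selects Grade 4, which looks deliberate. Precedent within the table is split 5 to 5. Appendix D records that the ALT/AST and nephritis rules were moved to a permanent stop at Grade 3 while the skin rule was not. Section 6.5.3 introduces Table 11 as general recommendations.

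The safeguards are also more than nominal. Section 6.5.1 asks for clinical judgment with medical monitor consultation whenever possible, immediate sponsor discussion of safety concerns, an investigator judgment that the participant is suitable to resume, and sponsor contact before restart after more than 28 days. A case meeting the seriousness criteria reaches the sponsor within 24 hours (Section 9.4). Sections 6.5.4 and 7.1.1 allow a stop on judgment.

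Most of this stands, and it rules out three stronger inferences that a reader might draw:

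- **That sites are told to restart after Grade 3 Stevens-Johnson syndrome.** They are not; restart is permitted, not required.
- **That the protocol contradicts itself.** It does not; nothing in it says that Grade 3 Stevens-Johnson syndrome must be stopped.
- **That footnote d tells sites to continue after a recurrence in someone who needed steroids.** It does not; the row still stops recurrent Grade 3, so the mismatch is an ambiguity.

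What remains is that, outside footnote b and the limits on delay, every barrier to re-exposure is discretionary. Section 6.5.1 directs that restart after immune-related events follow Section 6.5.3, so the table is operative. The ASCO/ESMO management reference is for events not detailed in the protocol, and skin events are detailed. The evaluation algorithms it also cites cannot be seen here.

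**Conclusion.** The point holds as a safety refinement worth considering. A confirmed first Grade 3 case that settles, in practice mainly within 14 days, may restart at full dose unless someone exercises discretion. Footnote b narrows the gap but responds to the course of the event, not to the diagnosis.

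The size is small: few or no cases in about 162 participants, and no effect on the primary analysis. Confidence is medium. The reading of the table is firm, but the view that a confirmed case should never be rechallenged is a clinical judgment that the documents neither state nor exclude.

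**What to change.** Amend Table 11 in three places.

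1. In the stop row, make the trigger *confirmed Stevens-Johnson syndrome (any grade)*. In the withhold row, change the Grade 3 entry to *Grade 3 (other than confirmed Stevens-Johnson syndrome)*. Both edits are needed; otherwise a confirmed Grade 3 case would match both rows.
2. For suspected Stevens-Johnson syndrome, allow resumption only once the diagnosis has been excluded, as the troponin block does for myocarditis.
3. In footnote d, delete the clause restricting the rule to first onsets managed without systemic steroids, so that the footnote matches its row.

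The cost is a few phrases at the next amendment and a site memo, with no change to design, sample size or analysis. The downside is that a rare participant with a resolved confirmed Grade 3 case, or with a suspected case that can be neither confirmed nor excluded, loses the option of rechallenge. The latest SAP amendment is dated March 2025, so dosing may be well advanced. If few participants remain on treatment, a memo may suffice, with the wording carried into later protocols.

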6.5.4. Criteria for Permanent Discontinuation of Study Treatment

The occurrence of unacceptable toxicity not caused by the underlying disease will require that the study treatment be permanently discontinued. Unacceptable toxicity is defined as follows:

- The occurrence of an AE that is related to study treatment that, in the judgment of the investigator or the sponsor's medical monitor, compromises the participant's ability to continue study-specific procedures or is considered to not be in the participant's best interest.
- A persistent AE requiring a delay of therapy for more than 4 weeks (28 days) unless a greater delay has been approved by the sponsor. See exception for irAEs related to study treatment below.
- An irAE that does not resolve within 12 weeks of the last dose of study treatment, or corticosteroids cannot be reduced to ≤ 10 mg/day prednisone or equivalent within 12 weeks.

See Section 7 for discontinuation procedures.

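### Table 11 footnote d ties the skin stop for recurrent Grade 3 to a first event that needed no systemic steroids, so recurrence after a steroid-treated first rash is not itself a stop

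*Protocol*

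**What the plan says.** The skin block of Table 11 (Protocol Section 6.5.3) works in steps.

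- **Grade 2:** no action on study treatment; the management column says "Manage with topical steroids with or without drug interruption".
- **Grade 3, persistent Grade 2, or suspected Stevens-Johnson syndrome:** withhold until Grade 1 or lower, and then "Study treatment can be resumed at same dose". The management column says "Administer corticosteroids per local practice followed by taper. Additionally, oral antihistamines such as diphenhydramine or famotidine".
- **Permanent discontinuation:** recurrent Grade 3 "after resuming study treatment or Grade 4 rash or confirmed Grade 4 Stevens-Johnson syndrome", or toxic epidermal necrolysis.

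Two footnotes qualify these rows. Footnote b, on the Grade 3 row, requires a permanent stop for "Participants with first onset of Grade 3 rash with desquamation, and/or mucosal involvement, requiring systemic steroids and not resolving or improving" to Grade 1 or lower within 14 days. Footnote d, on the recurrent Grade 3 trigger, reads "Refers to single recurrence after first onset of Grade 3 that did not require systemic steroids and participant recovered and resumed study treatment".

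Section 6.5.4 adds stops that apply to any event. One is "A persistent AE requiring a delay of therapy for more than 4 weeks (28 days) unless a greater delay has been approved" by the sponsor, with an exception for treatment-related irAEs. Another is "An irAE that does not resolve within 12 weeks of the last dose of study treatment, or corticosteroids cannot be reduced to" 10 mg/day of prednisone or equivalent within 12 weeks. A third rests on the judgment of the investigator or medical monitor.

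**The concern.** Footnote d is attached to the trigger in order to define it, and the definition leaves out anyone whose first Grade 3 rash needed systemic steroids. That reverses the expected order of severity. Take two participants who both recovered, resumed and then had a second Grade 3 rash. The one with the milder first course must stop. The one with the harder first course goes back to withholding and may be treated again. Section 6.5.1 does not permit dose modification and restarts drugs at the starting dose, so that further exposure would be at full dose.

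The omitted course also looks like the usual one under the table. The Grade 3 row directs corticosteroids with a taper, whereas topical steroids are the Grade 2 instruction. Read literally, the automatic stop would then cover only the less typical Grade 3 course.

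What is at stake is participant safety and consistent handling across sites. No efficacy inference is affected.

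**Working it through.** No figure in the plan is in dispute, so the check is a reading of the rules by case, followed by a short count.

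**1. Cases under the skin rows and footnotes**

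| First Grade 3 skin event | Later course | Rule that applies | Automatic stop? |
|---|---|---|---|
| No systemic steroids needed; recovered, resumed | Recurs at Grade 3 | Recurrent Grade 3 row with footnote d | Yes, at the recurrence |
| Systemic steroids; desquamation and/or mucosal involvement; not Grade 1 or lower by 14 days | None needed | Footnote b | Yes, at the first event |
| Systemic steroids; footnote b not met; recovered, resumed | Recurs at Grade 3 | Grade 3 row: withhold to Grade 1 or lower | **No** |
| Any | Grade 4 rash, confirmed Grade 4 Stevens-Johnson syndrome or toxic epidermal necrolysis | Permanent discontinuation row | Yes |

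The gap is the third line.

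**2. Could another rule supply the missing stop?**

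- Table 11, row for all other irAEs: it stops at recurrent Grade 3, but it covers events without their own block, and skin has one.
- Table 9 (Section 6.5.1.1): it covers events that are not immune-related, and it stops at the third occurrence, not the second.
- Section 6.5.4: its stops depend on judgment, length of delay, or failure to resolve or taper. None is triggered by recurrence.
- Section 7.1.1: it refers back to Section 6.5 for toxicity and otherwise relies on the investigator's view that continuing would be harmful.

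None makes the recurrence itself a stop.

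**3. Comparison within Table 11**

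Blocks: pneumonitis; diarrhea/colitis; AST/ALT/bilirubin/hepatitis; endocrinopathies (diabetes, hyperglycemia, thyroid, adrenal); hypophysitis; nephritis; skin; myocarditis; troponin increase; nervous system; all other irAEs. Total 11.

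- With a recurrence-based permanent stop: pneumonitis (recurrent Grade 2), colitis (recurrent Grade 3), skin (recurrent Grade 3), all other irAEs (recurrent Grade 3) = 4 of 11.
- Without one: 11 − 4 = 7.
- Of the 4, conditioned on steroid use at the first event: skin only = 1; unconditioned: 4 − 1 = 3.

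Colitis is the closest comparison. Its management column directs systemic corticosteroids at Grade 2 or 3, and any recurrent Grade 3 is still a stop.

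**4. Fixed limits that remain for the uncovered participant**

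- Section 6.5.4, irAE limit: 12 weeks × 7 = 84 days from the last dose, or 84 / 28 = 3 four-week cycles.
- Section 6.5.1: an interruption beyond 28 days needs sponsor approval, and the sponsor should be contacted before restart.

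A second Grade 3 rash that resolves, with steroids tapered to 10 mg/day or less, inside 84 days therefore meets no fixed stop, provided the sponsor agrees to any delay past 28 days.

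**5. Frequency**

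Section 2.2.3 lists dermatitis as an irAE in 1 of 40 participants on INCAGN02390 alone (1/40 = 2.5%). Section 2.2.4 lists no rash among the irAEs of 17 participants on the triplet. Neither is given by grade, so no expected number of affected participants can be calculated.

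**The case against.** The strongest reply is that this is loose drafting and not a real gap. The row itself is unqualified, and footnote d can be read as making clear that one recurrence is enough even after a mild first event, so that a harder first course would stop all the more. That may well be the intent. But the footnote is attached to define the term, and its words do not say so. Sites are left with two readings of a safety stop. Attaching the steroid clause to the recurrence instead of the first onset does not help either: the stop would then be limited to recurrences that need no systemic steroids.

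Second, individual safeguards remain. Section 6.5.1 calls for immediate discussion of safety concerns with the sponsor, restart decisions are made jointly with the medical monitor when needed, and Section 7.1.1 requires a stop if continuing would be injurious in the investigator's judgment. These stand and limit the harm. They rest on judgment or on sponsor contact, so they do not replace an automatic stop.

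Third, the Grade 3 skin row says corticosteroids without the word systemic, unlike pneumonitis and colitis, and footnotes b and d imply that only some first Grade 3 rashes need them. This is fair: the mention of a taper points to systemic use, but how common the uncovered course would be is inferred.

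Fourth, the count of 7 blocks with no recurrence stop mixes unlike cases. Hepatitis, nephritis (if drug-implicated), myocarditis and nervous system events already stop at the first Grade 3. That also stands; the informative comparisons are colitis and all other irAEs.

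Finally, Table 11 is introduced as general recommendations. Its instruction here is nonetheless to discontinue permanently, and investigators can be expected to work from it.

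**Conclusion.** The concern holds. As written, a Grade 3 skin recurrence after a steroid-treated first rash that resolved is not itself a stop, while the same recurrence after a first rash needing no systemic steroids is. Among the 4 Table 11 blocks with a recurrence stop, skin is the only one with this condition, and the documents give no reason for it.

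The point is minor and concerns patient safety. What is missing is the automatic stop at recurrence, not all protection: withholding, the 28-day sponsor check, the 84-day limits, the Grade 4 stops and clinical judgment remain. There is no effect on alpha, power or sample size, and the number of participants affected cannot be estimated.

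The conclusion rests on reading footnote d literally, as the definition of the row's trigger. Confidence is medium because the row heading alone could be taken to cover both histories.

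**What to change.** In footnote d, delete the six-word clause about systemic steroids (from the word that through the word steroids). The footnote would then refer to a single recurrence after a first Grade 3 onset in a participant who recovered and resumed treatment. Any Grade 3 skin recurrence after resumption becomes a permanent stop, as in the colitis and all-other-irAEs rows. The deletion removes the problem whichever noun the clause was meant to modify. Footnote b, the Grade 3 row and Section 6.5.4 stay as they are.

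The cost is six words in the next protocol amendment and possibly a few more discontinuations. Data collection, sample size, power and alpha do not change. If the sponsor did intend to leave recurrence after a steroid-treated rash to case-by-case judgment, the footnote should say so and give the reason.
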